Based on the demographic data presented above, we expect that the proportion of our final sample who are of minority ethnic origin will be small and preclude formal testing of minority status as a moderator of treatment effects. We will, however, explore this issue using descriptive statistics. We will compare characteristics of participants who completed vs. did not complete the intervention, to assess whether systematic factors (e.g., deprivation, ethnicity) are associated with engagement with MBT-PP. We will employ purposive sampling in the IPE elements of the trial in order that the experiences of minority ethnic groups are heard. We will take the race equity consultant's advice on whether we also need to hire researchers who are more representative of the communities we are trying to reach to conduct the interviews, and we will manage this within our budget if so.

Impact evaluation

Primary Research Question

RQ1 Does MBT-PP (compared to TAU) delivered to parents experiencing IPC lead to lower externalising and internalising behaviours in children aged 8-14 (as measured by the SDQ 'difficulties' scale)?

Secondary Research Questions

RQ2 Does MBT-PP (compared to TAU) delivered to parents experiencing IPC lead to higher wellbeing in children aged 8-14 (as measured by the Stirling Children's Well-being Scale)?

RQ3 Does MBT-PP (compared to TAU) delivered to parents experiencing IPC lead to lower IPC reported by parents (as measured by the O-Leary-Porter Scale)?

RQ4 Does MBT-PP (compared to TAU) delivered to parents experiencing IPC lead to lower IPC reported by children (as measured by the Children's Perception of Interparental Conflict Scale)?

RQ5 Does MBT-PP (compared to TAU) delivered to parents experiencing IPC lead to lower parent anger expression (as reported by the Dimensions of Anger Reactions-Revised)?

RQ6 Does MBT-PP (compared to TAU) delivered to parents experiencing IPC lead to higher mentalising ability in parents (as reported by the Parental Reflective Function Questionnaire)?

RQ7 Does MBT-PP (compared to TAU) delivered to parents experiencing IPC lead to more positive parenting (as measured by the Parenting Scale Short Form PS-8)?

RQ8 Does MBT-PP (compared to TAU) delivered to separated parents experiencing IPC lead to better parent emotional adaptation to relationship dissolution (as measured by the EARDA)?

Mechanisms of Action Research Questions

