RQ1 What are the key factors that influence successful delivery of and engagement with MBT-PP? (This will include collecting data on barriers and facilitators to implementation,

from both clients and therapists, including contextual and wider structural factors that might differentially affect minorities.)

RQ2 What compliance, contamination, and fidelity issues are present in the trial?

RQ3 What does the trial indicate about scalability? Can MBT-PP be delivered at scale?

Process RQs

RQ4 How does MBT-PP affect parents and children? What are the mechanisms of change?

Research methods

Throughout the IPE, we will purposively sample so that 50% of participants are from minority ethnic groups. The purpose of this sampling strategy is to ensure that we can understand how wider structural factors affect minority groups' engagement with the intervention and whether the intervention is sufficiently tailored and sensitive to minority groups.

We intend to conduct qualitative interviews with parents, MBT-PP therapists, Early Help practitioners and Gateway Leads to answer the IPE research questions. In each of these cases, participants will be provided with a specific participant information sheet and provide consent prior to participating in an interview. Interviews will be conducted by a member of the SHU research team who is experienced in conducting sensitive research and clinical interviews, or additional researchers if deemed appropriate by the race equity consultant. Interviews will either take place online using video conferencing software or by telephone, according to each participant's preference. The interviews will be semi-structured, following an interview schedule specific to the type of participant (parent, MBT-PP therapist or Early Help practitioner). Interviews will be audio-recorded and transcribed.

Parent interviews

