Qualitative interviews with parents with a sample of parents (n = 30) who have undergone MBT-PP will be used to explore engagement with MBT-PP and the psychological changes that parents experience as a result of MBT-PP. These interviews will use open questions to explore the impact of MBT-PP and how this was achieved, including whether parents experience a change in their mentalising abilities and ways of expressing anger, and whether and how the conflict in their co-parenting relationship has changed. For parents who are separated from their co-parent, the interviews will also explore how, if at all, MBT-PP has affected their emotional adaptation to the separation. Interviews will also use open questions to explore the issues that brought parents to MBT-PP (i.e., sources of conflict), how suitable MBT-PP was for their needs, and barriers and facilitators to engaging with MBT-PP.

Parents who have completed MBT-PP will be invited to take part in a remote interview about their experiences with MBT-PP. We will recruit participants from the three different LAs involved in this project, and where possible, we will purposively sample to ensure a broad demographic spread. Parents participating in an interview will be asked to confirm their sociodemographic details (e.g., age, ethnicity) collected as part of the baseline quantitative data. Parent interviews will explore barriers and facilitators to engaging with MBT-PP (RQ1), the activities undertaken as part of MBT-PP and how parents understand and use these (RQ2) and the psychological changes arising from MBT-PP (RQ4).

We will also interview a sample of parents who have undergone TAU (n = 15). These interviews will examine the nature and content of the support received in TAU, to support the fidelity assessment (RQ2), which is described below..

CYP interviews

Qualitative interviews with children of parents who have undergone MBT-PP will be used to explore children's experiences and their perceptions of IPC, and whether and how these have changed as a result of their parents undergoing MBT-PP.

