We will interview a sample of children (n = 20). A child-friendly participant information sheet will be provided to parents and children in advance. Informed consent for these children to participate will be sought from their parent, and assent will be sought from the children on the day of the interview. The Gateway Lead or Early Help practitioners will support children to access a remote interview with a member of the SHU research team. We anticipate that this might involve coordinating with the child's school or other community venue to ensure that the child can access the interview in a secure environment, where they will not be overheard by their parent and therefore will feel more able to speak freely. Child interviews will explore emotional/behavioural difficulties, wellbeing and their perceptions of IPC, and whether and how these have changed as a result of their parents undergoing MBT-PP (RQ4).

Therapist interviews

All therapists (n = 12) who provide MBT-PP for TR will be invited to participate in an interview. Therapist interviews will explore the activities that were carried out while working with MBT-PP clients (RQ2), barriers and facilitators to delivery of MBT-PP (RQ1) and perceptions of the impact of MBT-PP on clients (RQ4).

Treatment as usual provider interviews

We will conduct qualitative interviews with a sample of the LAs' practitioners who provide TAU (n = 12). All practitioners who provide TAU in this project will be invited to participate in an interview. These interviews will explore the activities that were carried out while providing TAU (RQ2) and the processes involved in identifying and referring parents to the trial (RQ3).

Gateway Leads interviews

We will interview the Gateway Leads (n = 3) to explore barriers and facilitators to conducting the trial (RQ3), specifically focussing on establishing referral pathways and buy-in from Early Help staff. Each of the Gateway Leads will be invited to participate, and will be provided with an information sheet in advance. Consent will also be obtained prior to participation.

Therapy recordings

To evaluate treatment fidelity, we will audio-record therapy sessions (and this will be stipulated in information sheets and consent forms), create a fidelity checklist (see below) and rate a proportion of therapy sessions for fidelity to the MBT-PP manual.

Treatment fidelity analysis

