Appendix A: Progress Criteria

Project Implementation

Area	Question	Assessment method	Progression criteria	Red Amber Green
1. Fidelity	Are therapy sessions being recorded?	Calculate percentage of therapy sessions delivered that are recorded.	% therapy sessions recorded	≥75%
				74-50%
				<50%
2. Eligibility/ Referral	Do enough referrals received meet the eligibility criteria?	Calculate the percentage of referrals received during months 9-16 ^a of the pilot that were eligible to take part in the study.	% referrals received that met the eligibility criteria	≥75%
				74-50%
				<50%
3. Dosage	Do MBT-PP clients attend enough therapy sessions?	Calculate percentage of clients who attended under six and over six MBT-PP sessions.	i) % clients who were discharged having attended less than six sessions of MBT-PP	≤25%
				26-50%
				>50%

			ii) % clients who were discharged having attended six or more sessions of MBT-PP	
≥75%
 
74-50%
 
<50%

4. Practitioner training	Have MBT-PP therapists received enough training?	Report amount of the five days post-qualification training on MBT-PP received by therapists.	Number of days' training in MBT-PP received by therapists	
All therapists have received full 5 days of training in MBT-PP prior to delivering MBT-PP.
 
One or more therapists have received only 3 or 4 days of training in MBT-PP prior to delivering MBT-PP.
 
One or more therapists have received less than 3 days of training in MBT-PP prior to delivering MBT-PP.

5. Supervision	Do MBT-PP therapists receive enough supervision?	Calculate mean hours of supervision per month for MBT-PP therapists.	Mean hours of supervision per month per MBT-PP therapist (pro-rata if part-time).	
All therapists delivering MBT-PP receive 1.5 hours per month
 
One or more therapists delivering MBT-PP receive less than 1.5 hours, but more than 59 minutes per month
 
One or more therapists delivering MBT-PP receive less than 1 hour per month.

6. Practitioner capacity	Do MBT-PP therapists have the capacity to work with clients as intended?	Calculate percentage of families (or individual parents, if parents are attending therapy separately) that are contacted by the therapist within 2 weeks of being allocated to a therapist.	% families contacted by a therapist within 2 weeks of being allocated a therapist	
≥75%
 
74-50%
 
<50%

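### The parent interviews on engagement invite only parents who completed MBT-PP, so Implementation RQ1 has no first-hand account from parents who did not start or left early

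*Protocol*

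**What the plan says.** Under Implementation Research Questions, the Protocol's RQ1 is "What are the key factors that influence successful delivery of and engagement with MBT-PP", with data to come "from both clients and therapists, including contextual and wider structural factors that might differentially affect minorities".

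The Parent interviews section gives the client part of this to one sample: a "sample of parents (n = 30) who have undergone MBT-PP will be used to explore engagement with MBT-PP". It adds that "Parent interviews will explore barriers and facilitators to engaging with MBT-PP (RQ1"). The invitation rule in the same section is "Parents who have completed MBT-PP will be invited to take part in a remote interview about their experiences with MBT-PP". The stated sampling aims are coverage of the three local authorities and a broad demographic mix. The Research methods paragraph adds that half of the participants in the process evaluation should come from minority ethnic groups. Attendance is not a sampling variable.

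Three other parts of the Protocol bear on engagement:

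- **Therapist interviews.** All 12 therapists are invited. Their RQ1 topic is "barriers and facilitators to delivery of MBT-PP (RQ1) and perceptions of the impact of MBT-PP on clients (RQ4").
- **Quantitative comparison** (Racial diversity and inclusion considerations): "We will compare characteristics of participants who completed vs. did not complete the intervention, to assess whether systematic factors" such as deprivation and ethnicity go with engagement. The Analysis section adds dropout analyses of compliant against non-compliant participants.
- **Progression criteria** (Appendix A). Criterion 3 counts "clients who were discharged having attended less than six sessions of MBT-PP". Criterion 8 counts families discharged before the end of the treatment protocol, as reported by therapists.

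The wording for the interview sample is not uniform. The Parent interviews section uses both *undergone* and *completed*, and Table 5 uses *received*. None of these is defined for interview sampling.

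**The concern.** RQ1 is about engagement, and the client interviews are restricted to people who engaged to the end. Parents who never attended, or who stopped after a few sessions, have met whatever barriers exist, and the rule gives them no route to an interview. The sample is selected on the behaviour that the question is meant to explain.

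Three of the plan's own aims are affected. The Research methods paragraph justifies the 50% minority-ethnic target by the need to see how structural factors affect minority groups' engagement, yet minority parents who disengage fall outside the frame. Table 5 expects parent interviews begun in the pilot to reveal problems that should be put right before the efficacy phase, and problems serious enough to make parents leave are the least likely to appear among those who stayed. The Qualitative Analysis section assesses acceptability to parents, and for MBT-PP this is the only parent sample it can use.

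**Working it through.** There is no stated figure to reproduce. The check sets the planned sources side by side and then sizes the excluded group.

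**Step 1. Which sources could give a non-completing parent's reasons?**

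| Source (Protocol) | What it gives | Own account from a non-completer? |
|---|---|---|
| MBT-PP parent interviews, n = 30 | Barriers and facilitators to engaging (RQ1), RQ2, RQ4 | Not under the stated invitation rule |
| Therapist interviews, n = 12 | Barriers to delivery (RQ1) | No; second-hand, with little or no contact where a family never attends |
| Completer and compliance comparisons | Characteristics associated with engagement | No; who, not why |
| Appendix A, criterion 8 | Therapist report of whether discharge was early | No |
| TAU parent interviews, n = 15 | RQ2 only | No |
| Gateway Lead interviews, n = 3 | RQ3 only | No |
| Risk register, attrition row (Table 6) | Promise to look into causes of attrition in the pilot | No method named; may mean attrition from the research |

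No row supplies it.

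**Step 2. Does the result depend on the meaning of *completed*?**

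- Finishing the treatment protocol (the sense of criterion 8): no parent from a non-completing family is invited.
- Reaching six sessions (the compliance rule in the Protocol and SAP): families that leave after session six but before the end can be invited; families with 0 to 5 sessions cannot.
- *Undergone* or *received*, read loosely: some partial attenders might be admitted; families that never started are still outside.

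On every reading, never-starters have no route to an interview.

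**Step 3. Illustrative size.** The documents give no actual non-completion rate, so the Appendix A limits serve as a range. Inputs:

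- MBT-PP families: 125 (SAP, Table 2; 250 × 0.50).
- Criterion 3 green limit: 25% of clients discharged with fewer than six sessions.
- Criterion 8 green limit: below 30% of families that attended session 1.
- Assumption: all 125 families attend session 1.

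The two limits overlap and have different denominators, so they are alternatives and are not added.

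- Families: 125 × 0.25 = 31.25, about 31. 125 × 0.30 = 37.5, so at most 37 while staying below 30%.
- Expected number in a proportionate sample of 30: 30 × 0.25 = 7.5, about 8. 30 × 0.30 = 9.
- At the upper end of amber (50%): 125 × 0.50 = 62.5, about 62 families; 30 × 0.50 = 15 interviews.
- Under the stated rule, with *completed* as finishing the protocol: 0 of 30.

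Families that never attend session 1 are outside these counts.

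**The case against.** The strongest case on the other side is that RQ1 was never meant to rest on these interviews alone. It draws on clients and therapists. Therapists treated the families who left early and can speak about them, and the quantitative comparisons show which families disengage. Looking for attrition that suggests an unacceptable intervention is a stated pilot aim, and the risk register promises an investigation of causes. Completers are asked openly about barriers and suitability, and some will have a co-parent who did not take part. *Completed* is also used loosely, so the strictest reading may not be the intended one. For RQ4, which asks how the therapy works, sampling people who had it is appropriate.

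Much of this stands. A reader might infer that RQ1 is answered only from completers and that non-engagement cannot be explained at all. The documents do not support that, because the therapist and quantitative inputs are real. A reader might also infer that a null or diluted ITT result could not be interpreted. That does not follow either: telling poor uptake from lack of effect rests on session counts (MBT-PP administrative data) and on the SAP's compliance definition and CACE analysis. Nor can the Appendix A limits be read as expected rates. They are tolerances, and the Protocol describes clinical unsuitability after allocation as only occasional. That completer interviews will necessarily look favourable is not shown.

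The objection does not supply the missing element. Therapists are asked about delivery, the comparisons give characteristics, and the risk register names no method. The parent's own reason for not starting or for leaving is still not collected.

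**Conclusion.** The point holds in a limited form. Followed as written, the invitation rule selects the client evidence for Implementation RQ1 on engagement, so findings on barriers and acceptability describe parents for whom the barriers were passable. RQ1 retains indirect evidence from therapists and from the quantitative comparisons.

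The shortfall is about 8 or 9 of the 30 interviews at the green limits. This assumes that rates sit at those limits, that all 125 families attend session 1, and that *completed* means finishing the treatment protocol; under the looser readings some partial attenders would be included and the shortfall would be smaller. This is an inexpensive improvement to the process evaluation.

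**What to change.** 1. Reconcile *undergone*, *completed* and *received* in the Parent interviews section and Table 5, and define the term used for interview sampling.
2. Change the interview frame to parents allocated to MBT-PP.
3. Within the same 30 interviews, purposively reserve about 8 for parents in families that did not start or attended fewer than six sessions, with a short variant of the topic guide on reasons. Families found unsuitable for risk reasons need not be in this quota.
4. Report RQ1 themes by attendance group.
5. If the quota is not met, state that client-side RQ1 findings apply to completers only.

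The cost is modest. No interviews are added, but the guide variant needs ethics review. Non-completers will be harder to reach, and the 50% minority-ethnic target still applies across the sample. About 22 completer interviews (30 − 8) remain for RQ4. The Protocol timeline runs process-evaluation data collection into May to December 2025.

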Please see risk register in Table 6.

Evaluation of Tavistock Relationships MBT-PP to improve child outcomes by reducing inter-parental conflict: a pragmatic efficacy randomised controlled trial with internal pilot

Evaluation protocol

Evaluating institution: Sheffield Hallam University

Principal investigator(s): [name]

Table 6. Risk register

Potential Risk Identification	Initial potential risk status			Preventative measures	Reducing the impact	Revised risk status		
	Likelihood	Impact	Risk			Revised Likelihood	Revised Impact	Revised Risk
Project specific risks								
Low recruitment	medium	medium	medium	Gateway Lead posts in each of the 3 LAs will oversee recruitment. Relationship building and significant project promotion activity by Tavistock Relationships with the LA staff will raise the profile of the project. In the event of low recruitment, we will explore the option of expanding to additional LAs.	Trial design can be adapted as necessary.	low	low	low
Attrition	medium	medium	medium	Encouraging compliance through strong rapport, advance notice and clear communication. Full	We use a dedicated project management/administrative support team to ensure a close	low	low	low

				investigation of causes of attrition in the in the pilot stage. Incentives for each questionnaire completed and an additional bonus incentive for completing all questionnaires.	positive working relationship with all stakeholders in the trial. Any attrition will be recorded using a consort flow diagram and taken into account at the analysis stage.			
Deliverer staffing difficulties	medium	high	medium	The deliverer should ensure that cover is available in the event of staff absence or departure	Each therapist could have a designated cover to pass clients onto in the event of illness or departure. Such staffing changes will be recorded and taken into account in the analysis as changes in therapeutic relationships may affect outcomes.	low	medium	low
Generic risks								
Covid 19 related disruption	High	medium	high	Team will closely monitor any evolving pandemic-related scenarios. Intervention delivery is all online so should not be affected. All staff are able to work remotely.	Team are used to working flexibly and responsively to changes to projects, timescales and participant needs. In consultation with YEF, team able to put forward revised evaluation plans based on various future scenarios	low	low	low
Staff absence/departure (e.g. due to long term illness)	low	high	medium	Team is of sufficient size, with any staff absences handled by colleagues who are highly experienced researchers. Centres involved have very low staff turnover and the same team see projects through from inception to completion in almost every instance, when this is not possible we have capacity to meet our commitments.	We have a large number of experienced research staff within SHU, who can be brought into the project with short notice if necessary. We feel this offers good contingency for unexpected staff absence.	low	low	low

Slippage and deadlines not met	low	high	medium	All team members experienced working on projects with tight deadlines. A well developed and agreed project plan would be followed. Robust and dedicated project management and progress monitoring plans mean that timelines are clearly understood with agreed responsibilities and deadlines. Regular team meetings will review progress and plan forward.	Projects are assessed continuously so potential problems are quickly identified. Regular contact will be maintained between SHU and YEF project managers to quickly anticipate and address emerging problems. Where a deadline is seen to be problematic this would be discussed at the first instance with YEF.	low	medium	low
--------------------------------	-----	------	--------	--	---	-----	--------	------------

Evaluation of Tavistock Relationships MBT-PP to improve child outcomes by reducing inter-parental conflict: a pragmatic efficacy randomised controlled trial with internal pilot Evaluation protocol

Evaluating institution: Sheffield Hallam University
Principal investigator(s): [name]

Timeline

Dates	Activity	Staff responsible/ leading
Jan-Feb 2023	
Set up phase.
 
Diversity training for whole team, preparation of all participant facing materials and data collection instruments, review of these by race equity consultant and YEF, application for ethical approval, piloting of materials with representative participants, data sharing agreements, safeguarding processes.
	AM & EC, with input from rest of Evaluation Team
March 2023-April 2024	
Pilot baseline data collection.
 
Referrals that come in from March-Dec will have post-intervention data included in the pilot study primary outcome analysis. Referrals coming in Jan-April will have baseline data only included in the analyses to address the aims of the pilot study regarding recruitment and acceptability.
	AM & EC, with input from rest of Evaluation Team

May-June 2024
	
Transition.
 
Evaluators prepare draft report on pilot, for submission end of May. YEF make progression decision by late June.
	
SD, JR, with input from rest of Evaluation Team.
 
AM & EC, with input from rest of Evaluation Team

July 2024-Dec 2024
	
Reflect on feedback from report. Make any alterations necessary to procedures.
 
Efficacy baseline data collection.
 
IPE data collection.
	
AM & EC, with input from rest of Evaluation Team

Jan-April 2025
	
Efficacy post-intervention data collection
 
IPE data collection.
	
AM & EC, with input from rest of Evaluation Team

May-Dec 2025
	
Complete 3 month follow up data collection.
 
Complete IPE data collection.
 
Analysis and reporting.
	
AM & EC, with input from rest of Evaluation Team.
 
SD, JR, with input from rest of Evaluation Team.

References

- Adamsons, K., & Pasley, K. (2006). Coparenting following divorce and relationship dissolution. In M. Fine & J. Harvey (Eds.), *Handbook of Divorce and Relationship Dissolution*, pp. 241-262. Mahwah, NJ: Lawrence Erlbaum
- Altman, D.G. & Bland, M.J. (2005) Statistics Notes: Treatment allocation by minimisation. *BMJ* 330 p843
- Arnold, D. S., O'leary, S. G., Wolff, L. S., & Acker, M. M. (1993). The Parenting Scale: a measure of dysfunctional parenting in discipline situations. *Psychological Assessment*, 5(2), 137. <https://doi.org/10.1037/1040-3590.5.2.137>
